13.2. Assessing Adverse Events

In conjunction with the medical monitor, the Investigator will evaluate adverse events to ensure the events are categorized correctly. Elements of categorization will include:

- Seriousness/Classifications (see definition in section 13.1).
- Causality or Relatedness – i.e. the relationship between the test article, study treatment or study procedures and the adverse event (not related, unlikely related, possibly related, or related - see definition in section 13.2.1).
- Adverse Event Severity – Adverse event severity is used to assess the degree of intensity of the adverse event (mild, moderate, or severe - see definition in section 13.2.2).
- Outcome – not recovered or not resolved, recovering or resolving, recovered or resolved with sequelae, recovered or resolved, death related to adverse event, or unknown.
- Actions Taken – none, temporarily discontinued, permanently discontinued, or other.

Clinical Study Protocol

Johnson & Johnson Vision Care, Inc.

13.2.1. Causality Assessment

Causality Assessment – A determination of the relationship between an adverse event and the test article. The test article relationship for each adverse event should be determined by the investigator using these explanations:

- Not Related- An adverse event that is not related to the use of the test article, study treatment or study procedures.
- Unlikely Related – An adverse event for which an alternative explanation is more likely, e.g. concomitant treatment, concomitant disease(s), or the relationship of time suggests that a causal relationship is not likely.
- Possibly Related – An adverse event that might be due to the use of the test article, or to the study treatment or study procedures. An alternative explanation, e.g. concomitant treatment, concomitant disease(s), is inconclusive. The relationship in time is reasonable. Therefore, the causal relationship cannot be excluded.
- Related – An adverse event that is listed as a possible adverse effect (device) or adverse reaction (drug) and cannot be reasonably explained by an alternative explanation, e.g. concomitant treatment of concomitant disease(s). The relationship in time is very suggestive, e.g. it is confirmed by de-challenge and re-challenge.

13.2.2. Severity Assessment

Severity Assessment – A qualitative assessment of the degree of intensity of an adverse event as determined by the Investigator or reported to him/her by the subject. The assessment of severity is made irrespective of test article, study treatment or study procedure relationship or seriousness of the event and should be evaluated according to the following scale:

- Mild – Event is noticeable to the subject but is easily tolerated and does not interfere with the subject's daily activities.
- Moderate – Event is bothersome, possible requiring additional therapy, and may interfere with the subject's daily activities.
- Severe – Event is intolerable, necessitates additional therapy or alteration of therapy and interferes with the subject's daily activities.

13.3. Documentation and Follow-Up of Adverse Events

The recording and documenting of adverse events (ocular and non-ocular) begin when the subjects are exposed to the test article, study treatment or study procedure. Adverse events reported before the use of test article, start of study treatment, or study procedures will be recorded as medical history. However, if the condition deteriorates at any time during the study it will be recorded and reported as an AE. Untoward medical events reported after the subject's exit from the study will be recorded as adverse events at the discretion of the Investigator.

Upon finding an adverse event, the Principal Investigator will document the condition in the subject record and in the eCRFs and complete the Adverse Event eCRF.

Complete descriptions of all adverse events must be available in the subject record. All Adverse Events including local and systemic reactions not meeting the criteria for "serious adverse events" shall be captured on the appropriate case report form or electronic data system.

Clinical Study Protocol **Johnson & Johnson Vision Care, Inc.**

All adverse events occurring while the subject is enrolled in the study must be documented appropriately regardless of relationship.

It is the Investigator's responsibility to maintain documentation of each reported adverse event. All adverse events will be followed in accordance with applicable licensing requirements. Such documentation will include the following:

- Adverse event (diagnosis not symptom).
- Drawings or photographs (where appropriate) that detail the finding (e.g., size, location, and depth, etc.).
- Date the clinical site was notified.
- Date and time of onset.
- Date and time of resolution.
- Adverse event classification, severity, and relationship to test articles, as applicable.
- Treatment regimen instituted (where appropriate), including concomitant medications prescribed, in accordance with applicable licensing requirements.
- Any referral to another health care provider if needed.
- Outcome, ocular damage (if any).
- Likely etiology.
- Best corrected visual acuity at the discovery of the event and upon conclusion of the event, if the AE is related to the visual system.

Upon discovery of an AE that is deemed 'possibly related' or 'related' to the test article or study procedures (whether related to the visual system or not), an AE review form [REDACTED] must be completed. Additional dated and initialed entries should be made at follow-up evaluations. Separate forms must be completed for each eye if the AE is bilateral.

In addition, if an infiltrate(s) is present, he/she will complete the Corneal Infiltrate Assessment eCRF. Where necessary, a culture of the corneal lesion will be collected to determine if the infection is microbial in nature. If cultures are collected, the date of culture collection and laboratory utilized will be recorded.

Changes in the severity of an AE shall be documented to allow an assessment of the duration of the event at each level of intensity to be performed. Adverse events characterized as intermittent require documentation of the onset and duration of each episode. Changes in the assessment of relationship to the Test Article shall also be clearly documented.

Subjects who present with an adverse event shall be followed by the Investigator, within licensure, until all signs and symptoms have returned to pre-treatment status, stabilized, or been satisfactorily resolved. If further treatment beyond licensure is required, the patient will be referred to the appropriate health care provider. The Investigator will use his/her clinical judgment as to whether a subject reporting with an adverse event will continue in the study. If a subject is discontinued from the study, it will be the responsibility of the Investigator to record the reason for discontinuation. The Investigator will also document the adverse event appropriately and complete the Adverse Event eCRF. Any subjects with ongoing adverse events related to the test article, study treatment or study procedures, as of the final study visit

Clinical Study Protocol

Johnson & Johnson Vision Care, Inc.

date, should be followed to resolution of the adverse event or until referral to an appropriate health care provider, as recommended by the Investigator. Non-ocular adverse events that are not related to the test article, study treatment, or study procedures may be recorded as “ongoing” without further follow-up.

13.4. Reporting Adverse Events

The Investigator will notify the Sponsor of an adverse event by e-mail, facsimile, or telephone as soon as possible and no later than 24 hours from discovery for any serious /significant adverse events, and 2 days from discovery for any non-significant adverse event. In addition, a written report will be submitted by the Principal Investigator to the IEC/IRB according to their requirements (section 13.4.2). The report will comment whether the adverse event was considered to be related to the test article, study treatment or study procedures.

13.4.1. Reporting Adverse Events to Sponsor

Serious/Significant Adverse Events

The Investigator will inform the sponsor of all serious/significant adverse events occurring during the study period as soon as possible by e-mail or telephone, but no later than 24 hours following discovery of the event. The Investigator is obligated to pursue and obtain information requested by the Sponsor in addition to that information reported on the eCRF. All subjects experiencing a serious/significant adverse event must be followed up and all outcomes must be reported.

When medically necessary, the Investigator may break the randomization code to determine the identity of the treatment that the subject received. The Sponsor and study monitor should be notified prior to unmasking the test articles.

In the event of a serious/significant adverse event, the Investigator must:

- Notify the Sponsor immediately.
- Obtain and maintain in the subject’s records all pertinent medical information and medical judgment for colleagues who assisted in the treatment and follow-up of the subject.
- Provide the Sponsor with a complete case history which includes a statement as to whether the event was or was not related to the use of the test article.
- Notify the IEC/IRB as required by the IEC/IRB reporting procedure according to national regulations.

Unanticipated (Serious) Adverse Device Effect (UADE)

In the event of an Unanticipated (Serious) Adverse Device Effect (UADE), the Investigator will submit a report of the UADE to the Sponsor and IEC/IRB as soon as possible, but no later than 24 hours after the Investigator first learns of the effect. This report is in addition to the immediate notification mentioned above.

The Sponsor must conduct an evaluation of the UADE and must report the results of the evaluation to FDA, the IEC/IRB and participating Investigators within 10 working days after the Sponsor first receives notification of the effect.

Clinical Study Protocol

Johnson & Johnson Vision Care, Inc.

Non-Serious Adverse Events

All non-serious adverse events, including non-serious adverse device effects, will be reported to the sponsor by the Investigator no later than 2 days from discovery.

13.4.2. Reporting Adverse Events to the Responsible IEC/IRB and Health Authorities

Adverse events that meet the IEC/IRB requirements for reporting must be reported within the IEC/IRB's written guidelines. Each clinical site will refer to and follow any guidelines set forth by their Approving IEC/IRB. Each clinical site will refer to and follow any guidelines set forth by their local governing Health Authorities.

The Sponsor will report applicable Adverse Events to the local health authorities according the written guidelines, including reporting timelines.

13.5. Event of Special Interest

13.5.1. Specific Requirements for Recording and Diagnosing Possible Microbial Keratitis

The signs of a presumed infectious ulcer (defined as progressive erosion of the corneal tissue) may include irregular focal infiltrates (>1 mm); active lesions with raised edges; significant diffuse infiltration; anterior corneal to mid-stromal involvement; erosion with overlying staining; conjunctival and lid edema; anterior chamber reaction (iritis); severe bulbar and limbal redness. Symptoms associated with a presumed infectious ulcer (microbial keratitis, MK) may include pain of rapid onset; severe redness; purulent or mucopurulent discharge; tearing; photophobia. For the purpose of reporting, per the ISO 11980, a presumed corneal ulcer which has any of the following characteristics should be reported as a serious adverse event:⁴⁸

- 1) Central (6 mm) or paracentral (8 mm) location;
- 2) Penetration of Bowman's membrane;
- 3) Infiltrate > 2 mm diameter
- 4) Associated with iritis \geq Grade 2;
- 5) Associated with any increase in intraocular pressure;
- 6) Culture positive for microorganisms
- 7) Increasing size of severity at subsequent visits.

In the event of any case of possible microbial keratitis (e.g., presence of an infiltrative lesion), the investigators shall provide complete descriptions of the event. A comprehensive description of diagnostic procedures is provided in [REDACTED].

The investigator shall record the following in the CRF:

- Presence and severity of pain;
- Presence and type of discharge;
- Presence of lid edema;
- Presence of chemosis;
- Pattern and grading of redness (bulbar/limbal);

Clinical Study Protocol **Johnson & Johnson Vision Care, Inc.**

- Characterization of infiltrates (size, shape, location, depth) on the Infiltrate Assessment Form;
- Characterization of the epithelial defect (size/depth);
- Involvement of surrounding cornea;
- Endothelial involvement;
- Grading of anterior chamber cell and flare

The investigator shall record the diagnosis and specific treatment on the Adverse Event Form. Where necessary, a culture of the corneal lesion will be collected to determine if the infection is microbial in nature. For example, if an overlying epithelial defect is present and any one of the conditions listed below is present when the infiltrate is first evaluated, the infiltrate must be cultured.

- Diameter greater than 1 mm
- Location within the central (6 mm) optical zone
- Purulent discharge
- Pain
- Photophobia
- Iris/Anterior chamber inflammation

Any corneal lesions meeting the criteria set forth above must be cultured as outlined in the Premarket Notification (510[k]) Guidance Document for Daily Wear Contact Lenses (Revised May 1994).²² Cultures will be collected with the Sponsor approved culture kits and sent to a study designated laboratory for analysis. The results will be communicated to the Investigator and the Sponsor. See [REDACTED] for specific procedures that should be followed for culturing of possible cases of infectious keratitis.

For other infiltrative events that do not meet the criteria as specified above, the investigators may culture the lesion when deemed appropriate. If cultures are collected, a source document note should be completed specifying the date of culture collection and laboratory utilized. An eCRF documenting this should be completed.

The following definitions will be used to classify whether the case is definite MK, probable MK, probably not MK, definitely not MK, or MK unrelated to contact lens wear.²³

- **Definite MK:** one or more central (6 mm) or paracentral (8 mm) corneal stromal infiltrates greater than 2 mm in size with pain rated more than mild, and one of the following:
 - anterior chamber reaction (iritis) Grade 2 or higher
 - mucopurulent discharge
 - positive corneal culture
- **Probable MK:** One or more corneal stromal infiltrates greater than 1 mm, with overlying epithelial defect, with pain more than mild, and at least one of the following additional criteria:
 - anterior chamber reaction;
 - mucopurulent discharge;
 - positive corneal culture;

Clinical Study Protocol

Johnson & Johnson Vision Care, Inc.

- aggressive treatment consistent with standard of care for MK in North America (choice of medication, high frequency dosing of long duration to resolution).
- **Probably not MK:** not meeting any of the above specified MK definitions.
- **Definitely not MK:** not meeting any of the above specified MK definitions and with significant evidence that suggests non-infectious etiology (e.g., reduction in severity without pharmacologic treatment).
- **MK unrelated to contact lens wear:** cases such as *Herpes simplex* keratitis or *Staphylococcal* marginal keratitis, where, in the judgment of the panel, the etiology is unrelated to the wear of contact lenses.

13.5.2. Loss of Best Sphero-cylindrical Corrected Visual Acuity without Physical Cause

At the final study visit, if it is found that best sphero-cylindrical corrected visual acuity (BSCVA) of a subject is less than 20/25 (0.1 logMAR) in either eye and is more than 1.5 lines worse than that was measured at baseline without any physical cause (confirmed through up to 3 repeated independent measures to rule out potential measurement errors or variations), an adverse event will be filed. The subject will be followed until the best corrected visual acuity is no more than 1.5 lines worse than baseline or is stabilized before being discontinued from the study. A decrease of more than 1.5 lines of BSCVA is considered a significant change. This criterion is established based on the 95% limits of agreement of repeated measures of visual acuity in children.²⁴ It is not anticipated that development of amblyopia (defined as a reduction of BSCVA to 20/30 or worse or a two-line difference between the two eyes, in the absence of pathology²⁵⁻²⁷) will occur while wearing the investigational soft contact lens. Upon identifying the first confirmed case of amblyopia during the course of the study, the event will be investigated and followed according to procedures specified for an Unanticipated Adverse Device Effect (section 11 and section 13.1).

13.6. Reporting of Pregnancy

Subjects reporting pregnancy (by self-report) during the study will be discontinued after the event is recorded as an Adverse Event. Once discontinued, pregnant participants and their fetuses will not be monitored for study related purposes. Pregnant participants are not discontinued from contact lens or solution related studies for safety concerns, but due to general concerns relating to pregnancy and contact lens use. Specifically, pregnant women are discontinued due to fluctuations in refractive error and/or visual acuity that occur secondary to systemic hormonal changes, and not due to unforeseen health risks to the mother or fetus.

14. STATISTICAL METHODS

14.1. General Considerations

Statistical Analysis will be undertaken by the sponsor or under the authority of the sponsor. A general description of the statistical methods to be implemented in this clinical trial is outlined below. More details will be included in the stand-alone Statistical Analysis Plan (SAP). The SAP will be developed and finalized prior to database lock.

Clinical Study Protocol

Johnson & Johnson Vision Care, Inc.

All data summaries and statistical analyses will be performed using the SAS software Version 9.4 or higher (SAS Institute, Cary, NC).²¹ Throughout the analysis of data, the results for each subject/eye will be used when available for summarization and statistical analysis. Unscheduled visits will be summarized separately and will be excluded from the statistical analysis.

Summary tables (descriptive statistics and/or frequency tables) will be provided for all baseline variables, efficacy variables and safety variables as appropriate. Continuous variables will be summarized with descriptive statistics (n, mean, standard deviation (SD), median, minimum and maximum). Frequency count and percentage of subjects or eyes within each category will be provided for categorical data.

14.2. Sample Size Justification

The plan is to enroll approximately 75 eligible subjects with a minimum of 50 subjects targeted to compete the study. Given no historical data is available for the Control lens (MiSight 1 Day), a power analysis for the primary endpoint was conducted to estimate statistical power based on historical data for the Test lens (EMO-118) under various scenarios with different assumptions and sample sizes.

EMO-118 and EMO-114 lenses were evaluated in a historical study (████████) with a parallel group design. Table 7 below presents the descriptive statistics of distance binocular logMAR VA under bright HLHC at 1-week follow-up observed from ██████████

Table 7: Descriptive Summaries of Binocular LogMAR Visual Acuity at 1-week Follow-up from ██████████ – Per Protocol Subjects

	EMO-114	EMO-118
Number of subjects	42	41
Mean (SD)	-0.12 (0.083)	-0.08 (0.084)

SD = standard deviation

Considering different number of subjects to complete the study (i.e., 40, 50, or 60), a power analysis was conducted for the primary hypothesis based on the assumptions for correlation between repeated measures, standard deviation for the Control lens, and effect size (i.e., mean difference between the Test and the Control). It was assumed that the standard deviation of MiSight is the same EMO-118 with respect to distance binocular HLHC logMAR VA. Power was estimated using a paired sample *t*-test with a 2-sided type I error rate of 5% and non-inferiority margin of 0.05. The calculation was performed using the POWER procedure in SAS Version 9.4. Table 8 below shows the estimated statistical power under different scenarios. Given time and resource constraints, fifty subjects have been considered as the optimal number which demonstrated an acceptable level of statistical power under most assessed scenarios. Therefore, the plan is to enroll approximately 75 eligible subjects with a minimum of 50 subjects targeted to compete the study.

Clinical Study Protocol
Johnson & Johnson Vision Care, Inc.

Table 8: Power Analysis for the Primary Hypothesis

Endpoint	Standard Deviation	Mean Difference (EMO-118 - MiSight)	Correlation	Completed Subjects	Power
Distance Binocular HLHC LogMAR VA	0.084	0	0.3	40	87.3%
				50	93.7%
				60	96.9%
		0.01	0.5	40	95.6%
				50	98.5%
				60	99.5%
		0.01	0.3	40	69.9%
				50	79.7%
				60	86.6%
		0.01	0.5	40	83.6%
				50	91.0%
				60	95.2%

14.3. Analysis Populations

The following analysis populations will be defined and used in the analysis and presentation of the data.

Safety Population:

All subjects who are administered any test article excluding subjects who drop out prior to administering any test article. At least one observation should be recorded. Subjects will be analyzed as per treatment received.

Per-Protocol Population:

All subjects who successfully complete all visits and do not substantially deviate from the protocol as determined by the trial cohort review committee prior to database hard lock. Justification for the exclusion of subjects with protocol deviations from the per-protocol population set will be documented in a memo to file. See section 10 for definition and examples of major deviations.

Intent-to-Treat (ITT) Population:

All randomized subjects regardless of actual treatment and subsequent withdrawal from the study or deviation from the protocol. At least one observation should be recorded. Subjects will be analyzed as per randomized treatment.

Clinical Study Protocol

Johnson & Johnson Vision Care, Inc.

14.4. Level of Statistical Significance

The planned primary analysis for this study will be conducted with a two-sided type I error rate of 5%. Each exploratory analysis will be conducted with a two-sided type I error rate of 5%.

14.5. Primary Analysis

Primary Efficacy Endpoint

Binocular Distance (4m) logMAR Visual Acuity (VA)

Non-inferiority of the EMO-118 compared to the MiSight lens with respect to the primary endpoint of distance binocular HLHC logMAR visual acuity will be assessed on the Per-protocol population (PP).

The distance binocular logMAR VA under HLHC will be analyzed using a linear mixed model at the follow-up evaluation. The model will include lens type, lens sequence, period, and first-order carryover as fixed effects and interaction between lens type and period will be evaluated. Other subject characteristics such as age, gender and race will be included as fixed covariates when appropriate. Site will be included in the model as a random effect (G-side). The covariance of residuals between measurements from different periods within the same subject (R-side) will be modeled using Unstructured (UN) covariance structure. If the model does not converge, the compound Symmetry (CS) covariance structure will be considered. The Kenward and Roger method will be used for the denominator degree of freedom.²⁸

Hypothesis Testing

The null and alternative hypotheses for testing non-inferiority of the EMO-118 lens relative to the MiSight lens with respect to logMAR visual acuity are as follows:

$$H_0: \mu_{EMO118} - \mu_{MiSight} \geq 0.05$$
$$H_A: \mu_{EMO118} - \mu_{MiSight} < 0.05$$

Where, μ_{EMO118} represents the mean logMAR VA score for the EMO-118 lens and $\mu_{MiSight}$ represents the mean logMAR VA score for the MiSight lens. Non-inferiority will be declared if the upper bound of the 2-sided 95% confidence interval (CI) of the mean difference (EMO-118 – MiSight) is less than 0.05.

Primary Safety Endpoint

Primary safety endpoint will be evaluated by tabulations of contact lens related (i.e., related and possibly related) serious and significant ocular adverse events and will be summarized by treatment across all visits. The tables will present the number and percentage of eyes and subjects by diagnosis and sorted by decreasing frequency based on the total number of reports.

Additionally, all ocular and non-ocular adverse events will be summarized by seriousness (i.e., ocular AEs by serious, significant and all other ocular AEs, and non-ocular AEs by serious and non-serious), relatedness, severity and diagnosis. A listing of all adverse events including all

Clinical Study Protocol

Johnson & Johnson Vision Care, Inc.

information of an event (e.g., diagnosis, duration, treatment and resolution status) will be provided.

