4.2. Study Design Rationale

This study is to evaluate logMAR visual performance of three soft contact lenses featuring myopia control optical designs using a 3x3 crossover design. Crossover designs are well-established and expose subjects to multiple treatments during different time periods. This design is cost effective and efficient since it eliminates between-subject variability from the treatment comparisons. A limitation of crossover design is the potential for carryover effects between treatments. Since the primary endpoint of logMAR visual acuity is an objective measure, a carryover effect is less concerning. All subjects will begin with a run-in period

Clinical Study Protocol

Johnson & Johnson Vision Care, Inc.

using a single vision contact lens design to allow both new and existing contact lens wearers to enter the study and acclimate to a similar contact lens design.

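### The primary model adjusts for first-order carryover, which raises the variance of EMO-118 minus MiSight by 25%; Table 8 takes power from a paired t-test without that term, so the stated power at 50 completers is not delivered

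*Combined protocol and SAP*

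**What the plan says.** Section 14.5 gives the primary analysis as a linear mixed model on the per-protocol population: "The model will include lens type, lens sequence, period, and first-order carryover as fixed effects". Residual covariance within subject is unstructured, with compound symmetry as the fallback. "Non-inferiority will be declared if the upper bound of the 2-sided 95% confidence interval (CI) of the mean difference" (EMO-118 minus MiSight) is below 0.05 logMAR. The lens-by-period interaction is to be evaluated and covariates enter where appropriate, but the carryover term is unconditional: no rule drops it.

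Section 14.2 obtains power another way. "Power was estimated using a paired sample" t-test, with a "2-sided type I error rate of 5% and non-inferiority margin of 0.05". The per-lens SD is 0.084, from EMO-118 in a historical study (Table 7), and "It was assumed that the standard deviation of MiSight is the same EMO-118". Table 8 covers correlations 0.3 and 0.5, true differences 0 and 0.01, and 40, 50 or 60 completers. On that basis, "fifty subjects have been considered as the optimal number which demonstrated an acceptable level of statistical power under most assessed scenarios". No allowance is made for terms in the planned model.

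Section 5.1 fixes the design: three lenses, three periods, and all six sequences in every block. Section 4.2 names carryover as a limitation of crossover designs but says that for this endpoint "a carryover effect is less concerning".

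**The concern.** A paired t-test uses the simple within-subject difference between two lenses. The planned model estimates that difference after adjusting for the lens worn in the preceding period. Balance for first-order carryover means that each lens follows each other lens equally often. It does not make lens and carryover effects orthogonal, because no lens ever follows itself. The adjustment therefore costs precision, and Table 8 does not count that cost.

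What is at stake is the basis for choosing 50. Section 2.3 makes the study objective depend on this one hypothesis. If the planned model has less power than Table 8 shows, a truly non-inferior EMO-118 is more likely to miss the 0.05 bound than the plan tells its readers.

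**Working it through.** **Inputs.** From section 14.2 and Table 8: SD 0.084 for both lenses, correlation r = 0.3 or 0.5, true difference d = 0 or 0.01, margin 0.05, two-sided 5% (upper 97.5% bound), n = 50. From section 5.1: six sequences, equally replicated. From section 14.5: lens, sequence, period and carryover fixed.

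**Step 1: reproduce Table 8.** The variance of the mean paired difference is 2 × 0.084² × (1 − r)/n. Power is the probability that a noncentral t with n − 1 df and noncentrality (d − 0.05)/SE falls below −t(0.975, n − 1).

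- r = 0.3, n = 50: SE = 0.084 × √(1.4/50) = 0.01406. Noncentrality is −3.557 at d = 0 (power 93.66%) and −2.846 at d = 0.01 (power 79.66%).
- r = 0.5, n = 50: SE = 0.084 × √(1/50) = 0.01188. Noncentrality is −4.209 at d = 0 (power 98.48%) and −3.367 at d = 0.01 (power 91.00%).

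All 12 cells of Table 8 reproduce to within 0.1 point.

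**Step 2: cost of the carryover term.** Take one subject per sequence (six subjects, 18 observations) and compound symmetry. Because sequence is fixed, only within-subject information bears on lens and carryover. On the contrast scale:

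- Lens information: each lens appears 18/3 = 6 times and is orthogonal to subject and period, giving 6.
- Lens by carryover: there are 12 transitions over 6 ordered pairs, so each lens follows each other lens twice and itself never, giving −2.
- Carryover information: each lens is carried forward 12/3 = 4 times. A subject's carryover total is minus the effect of the lens worn third, so removing subject means takes off 2 × 3 × (1/3)² = 2/3, leaving 10/3.
- Lens information after adjusting for carryover: 6 − (−2)²/(10/3) = 6 − 1.2 = 4.8.

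The variance ratio is 6/4.8 = 1.25, whatever r is. A generalized least squares calculation on the full design matrix gives 1.00 with lens, sequence and period, and 1.25 once carryover is added. At n = 50, which is not a multiple of six, the ratio to the paired-t variance is 1.23 to 1.27, depending on which two sequences hold the extra subjects.

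**Step 3: power at 50 completers with the 1.25 factor.** SE becomes 0.01571 (r = 0.3) or 0.01328 (r = 0.5). The range runs from n − 1 = 49 df to 100 − 6 = 94 df, the latter counting two parameters each for period, lens and carryover. The simulation has 20,000 trials per row with sequences split 9, 9, 8, 8, 8, 8.

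| d | r | Table 8, n = 50 | With carryover, n = 50 | Simulated | Table 8, n = 40 |
|---|---|---|---|---|---|
| 0 | 0.3 | 93.7% | 87.7–88.3% | 88.4% | 87.3% |
| 0 | 0.5 | 98.5% | 95.8–96.1% | 96.1% | 95.6% |
| 0.01 | 0.3 | 79.7% | 70.4–71.2% | 71.3% | 69.9% |
| 0.01 | 0.5 | 91.0% | 83.9–84.6% | 85.0% | 83.6% |

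The delivered figures lie close to the plan's own entries for 40 completers, as 50/1.25 = 40 implies. At equal df the confidence interval is √1.25 = 1.118 times as wide. At 49 df its half-width goes from 2.010 × 0.01406 = 0.0283 to 2.010 × 0.01571 = 0.0316 for r = 0.3.

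**Step 4: completers needed.** Raising n with the 1.25 factor and n − 1 df until Table 8's figures for 50 return gives 62 in all four scenarios (50 × 1.25 = 62.5).

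**The case against.** The arithmetic is not in dispute; the case on the other side concerns weight, conditions and remedy.

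- **Most scenarios stay above 80%.** Section 14.2 claims only acceptable power in most scenarios and sets no threshold. If 80% is assumed, the same three scenarios pass with or without carryover, and the one that fails was already just below at 79.7%. This stands as a limit on the consequence. It does not make the printed figures right for the planned model.
- **Fifty is a minimum.** About 75 are to be enrolled, and 62 completers would mean losing 13 of 75, or 17%. So the shortfall applies at the completer number on which section 14.2 rests, and it closes if retention is good. But the primary analysis set is per-protocol, which may be smaller than the set of completers, and dropouts are not replaced.
- **The 25% is conditional.** It is exact for compound symmetry and equal sequence sizes, whereas section 14.5 tries an unstructured covariance first. This condition should be stated. Compound symmetry is what one SD and one correlation imply, and one Toeplitz-type alternative (correlations 0.5 and 0.3) gave a larger ratio, 1.39.
- **Modelling carryover is defensible.** The design was chosen for carryover balance, and the washout at the visit is 10 minutes. Dropping the term trades variance for possible bias. This stands, so removing it is a choice and not a necessary correction.
- **No harm to validity.** Type I error and the confidence interval are sound, and the cost is a greater risk of a failed claim. Section 14.1 also defers detail to a stand-alone SAP, but nothing supplied removes the term.

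**Conclusion.** The concern holds. Table 8 is correct for a paired t-test, but section 14.5 plans a different analysis, and section 14.2 offers the figures as power for the primary hypothesis. Under Table 8's own assumptions, the carryover adjustment multiplies the variance of the primary contrast by 1.25. It lowers power at 50 completers by about 2 to 3 points in the most favourable scenario and 8 to 9 points in the least favourable. In the latter, the chance of missing non-inferiority rises from about 20% to about 29–30%.

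This rests on compound symmetry, near-equal sequence sizes, sequence as a fixed effect, and carryover kept in the model as section 14.5 states. If sequence were not fixed, the ratio would still be about 1.23 (r = 0.3) or 1.24 (r = 0.5). If the lens-by-period interaction were also retained, the ratio would be 1.33 and the weakest scenario would fall to about 68%. The plan only says that interaction will be evaluated, so the conclusion does not depend on it.

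**What to change.** Make the power statement and the primary model agree, before database lock.

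- **Keep carryover and restate the power.** Recalculate Table 8 for the section 14.5 model; at 50 completers the entries become about 88%, 96%, 71% and 84%. Revise the section 14.2 sentence that calls 50 optimal, and say that about 62 per-protocol completers would be needed for the figures now printed. This follows directly from the mismatch and costs only a less favourable table.
- **Or move carryover out of the primary model.** Keep lens, sequence and period in section 14.5, and pre-specify carryover and lens-by-period as sensitivity analyses. This restores Table 8 exactly in the balanced design and costs one sentence in section 14.5 and the matching text in the SAP. It accepts possible bias if carryover exists, so the choice should be argued from section 4.2 and made without sight of the data.

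Neither option needs more subjects.
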